15 ADMINISTRATIVE, ETHICAL, REGULATORY CONSIDERATIONS	29
15.1 Protocol Amendments	30
15.2 Institutional Review Boards and Independent Ethics Committees	30
15.3 Informed Consent Form	30
15.4 Publications	31
15.5 Investigator Responsibilities	31
16 APPENDICES	35
Appendix 1: Patient instructions	35
Appendix 2: Treatment diary	35
Appendix 3: Visit #1 CRF	35
Appendix 4: Visit #2 CRF	35

LIST OF ABBREVIATIONS

AE	adverse event
CFR	Code of Federal Regulations
CRF	case report form
DMC	Data Monitoring Committee
DSMB	Data Safety Monitoring Board
FDA	Food and Drug Administration
GCP	Good Clinical Practice
cGVHD	chronic graft versus host disease
HIPAA	Health Insurance Portability and Accountability Act of 1996
ICF	informed consent form
ICH	International Conference on Harmonisation
IEC	Independent Ethics Committee
IRB	Institutional Review Board
OLP	Oral lichen planus
PI	Principal Investigator
SAE	serious adverse experience

PROTOCOL SYNOPSIS

TITLE	DEXAMETHASONE SOLUTION AND DEXAMETHASONE IN MUCOLOX™ FOR THE TREATMENT OF ORAL INFLAMMATORY ULCERATIVE DISEASES
SPONSOR	Professional Compounding Centers of America
FUNDING ORGANIZATION	
NUMBER OF SITES	1
RATIONALE	Topical steroid therapy is considered the first line of treatment for Oral Inflammatory Ulcerative Diseases with current treatment regimens requiring multiple application or rinses daily. Although topical steroid therapy can be successful for most patients, the treatment schedule can be challenging to maintain. There is therefore considerable interest in developing new and more effective therapies that require less frequent applications. The possibility of having a treatment agent that is safe, easy to use, and cost effective, with potentially greater efficacy than the current standard of care available topical steroid solutions would be ideal. Using Mucolox™ as a vehicle to deliver topical dexamethasone to the oral mucosa has the potential to effectively prolong contact time between the medication and mucosa, leading to improved clinical outcomes due to the need for less frequent application. This technology would help to more efficiently achieve high drug concentrations locally. By possibly shortening the frequency and time of topical therapy and improving patient compliance, this may translate to greater therapeutic benefit.
STUDY DESIGN	This is a randomized, phase 2 study.
PRIMARY OBJECTIVE	The primary objective of this study is to determine the clinical efficacy and tolerability of compound dexamethasone at 0.5 mg/5 mL in Mucolox™ for the treatment of Oral Inflammatory Ulcerative Diseases as measured by a reduction in oral symptoms between patients treated with compounded dexamethasone 0.5mg/5ml solution in Mucolox™ (group A) and patients treated with topical commercial dexamethasone 0.5mg/5ml solution only (group B).
SECONDARY OBJECTIVES	The secondary objectives are: 
 • To determine the clinical improvement in clinician-reported outcome measures achieved by treatment with topical compounded dexamethasone at 0.5 mg/5 mL in Mucolox™ compared to commercial dexamethasone 0.5mg/5ml solution alone. • To assess the tolerability of Oral Inflammatory Ulcerative Diseases as measured with the 14-item Oral Health Impact Profile (OHIP-14).
NUMBER OF SUBJECTS	30
SUBJECT SELECTION	Inclusion Criteria:

CRITERIA
	
Age 18 years and older.
 
Patients with symptomatic biopsy proven Oral Inflammatory Ulcerative Diseases (worst VAS sensitivity score ≥ 7 over the last week).
 
Ability to understand and the willingness to sign a written informed consent document.
 
Exclusion Criteria: Patients already on topical or systemic steroids.
 
Inability to comply with study instructions.
 
Uncontrolled intercurrent illness or psychiatric illness/social situations that would limit compliance with study requirements.
 
VAS sensitivity score < 7.
 
Pregnant women. A urine pregnancy test will be performed for women of child bearing potential.
 
Allergy to fluconazole
 
Patients on medications that have a strong interaction with fluconazole
 
Patients with advanced liver disease

TEST PRODUCT, DOSE, AND ROUTE OF ADMINISTRATION
	
Dexamethasone 0.5 mg/5mL in Mucolox compounded oral solution swish and spit TID for 4 weeks

CONTROL PRODUCT, DOSE AND ROUTE OF ADMINISTRATION
	
Dexamethasone 0.5 mg/5mL (NDC 00054-3177-63; Roxane Laboratories, Columbus, OH 43216-6532) oral solution swish and spit TID for 4 weeks

DURATION OF SUBJECT PARTICIPATION AND DURATION OF STUDY
	
Subjects will be on study for up to 28 days
 
Screening: day 0
 
Treatment: 28 days
 
Follow-up: Day 28 \pm 5 days
 
The total duration of the study is expected to be 4 weeks.

CONCOMITANT MEDICATIONS	Allowed: all Prohibited: none
EFFICACY EVALUATIONS	
PRIMARY ENDPOINT	
 Change from pre to post treatment in each subject's subjective sensitivity score (0-10) evaluated at baseline and 4 weeks post treatment for each arm. We will also compare changes of the daily subject's subjective sensitivity score (0-10) over time for each arm.
SECONDARY ENDPOINTS	
 The secondary endpoints include the evaluation of objective data using the REU scoring system and the oral health related quality of life using the OHIP-14.
OTHER EVALUATIONS	None
SAFETY EVALUATIONS	The safety of participants and the overall study will be monitored continuously throughout the study period. At the 4 week visit, evaluating doctors will review the participants' diaries for self-reported adverse events.
PLANNED INTERIM ANALYSES	When approximately 50% of patients have completed the study, an interim analysis for safety will be conducted by an independent data monitoring committee. Serious adverse events will be monitored by the committee on an ongoing basis throughout the study.
STATISTICS Primary Analysis Plan	Pre-to-post treatment improvement will be assessed using McNemar's test within each arm. The REU scores will be summarized descriptively for each arm at pre-treatment, post-treatment, and pre-to-post treatment change. The pre-to-post treatment change will be compared between the arms using either student's t-test or Mann-Whitney test, depending on the distribution of the data.
Rationale for Number of Subjects	The sample size was calculated to ensure at least 80% power and two-sided alpha of 0.05 in detecting a t difference of 2.0 points oral pain on an 11 point scale (VAS 0-10) between Arm A and B.

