3 STUDY OBJECTIVES

3.1 Primary Objective

The objective of this single center, 4-week, open label randomized, phase II study is to determine the clinical efficacy and tolerability of compound dexamethasone at 0.5 mg/5mL in Mucolox™ for the treatment of Oral Inflammatory Ulcerative Diseases as measured by a reduction in oral symptoms between patients treated with compounded dexamethasone 0.5mg/5ml solution in Mucolox™ (group A) and patients treated with commercial topical dexamethasone 0.5mg/5ml solution only (group B).

Completion of this study will establish important data on the efficacy of topical steroid therapy when combined with a carrier and delivery system such as Mucolox™.

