9.2.3 Patient Reported Outcomes

Subjective assessments of subjects' oral symptoms will be obtained by using instruments from the NIH consensus documents for oral cGVHD, a condition that is very similar to other Oral Inflammatory Ulcerative Diseases (see Appendix 3 &4). These include report of mouth sensitivity at rest and sensitivity with stimulation (e.g. eating) on an eleven point scale. For the primary endpoint the worst sensitivity in the past week will be used. The clinician seeing the subject will

complete these forms at each study visit. Patients will also report daily sensitivity on an eleven point scale (see Appendix 2). Tolerability and compliance will also be evaluated, and a patient reported global assessment of overall improvement will be evaluated at the four-week visit.

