13 STATISTICAL METHODS AND CONSIDERATIONS

Prior to the analysis of the final study data, a detailed Statistical Analysis Plan (SAP) will be written describing all analyses that will be performed. The SAP will contain any modifications to the analysis plan described below.

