13.1.1 Analysis of Primary Endpoints

VAS scores will be summarized descriptively for each arm at pre-treatment, post-treatment, and pre-to-post treatment change. The pre-to-post treatment change will be compared between the arms using either Student's t-test or Mann-Whitney test, depending on the distribution of the data.

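### The synopsis row for the primary analysis carries secondary-endpoint text: it analyses REU, adds a McNemar test with no stated variable, and never names the 0-10 sensitivity score

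*Combined protocol and SAP*

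**What the plan says.** The synopsis row for the primary analysis has three sentences.

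1. "Pre-to-post treatment improvement will be assessed using McNemar's test within each arm". No variable is named.
2. REU scores are to be described by arm before treatment, after treatment and as change.
3. The change is to be compared between arms by t-test or Mann-Whitney test, according to its distribution.

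Other parts of the document describe the primary analysis differently.

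- **Synopsis, primary endpoint:** the outcome is how far the 0-10 sensitivity score moves between baseline and week 4. REU and OHIP-14 are listed as secondary.
- **Synopsis, sample-size row:** the trial is sized for "detecting a t difference of 2.0 points oral pain on an 11 point scale (VAS 0-10) between Arm A and B".
- **Section 3.1:** efficacy is judged "as measured by a reduction in oral symptoms between patients treated with" one formulation or the other.
- **Section 9.2.3:** "For the primary endpoint the worst sensitivity in the past week will be used".
- **Section 13.1.1:** the change in VAS score is "compared between the arms using either Student's t-test or Mann-Whitney test, depending on the distribution of the data". There is no McNemar test.
- **Section 13:** a separate SAP will follow, and "The SAP will contain any modifications to the analysis plan described below".

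**The concern.** The row headed as the primary analysis and the section headed as the primary analysis name different variables. An analyst or reader who works from the synopsis would take REU change as the primary result, together with a McNemar test that cannot be run on the primary endpoint. The trial is open label (Section 8.2), REU is scored by a clinician, and sensitivity is reported by the patient, so the two could give different answers. With two statements on file, it could be disputed afterwards which result was the primary one. No section says which statement prevails.

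**Working it through.** **Step 1. Trace each sentence of the row.**

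| Synopsis row | Match in Section 13.1.2 | Section 13.1.1 |
|---|---|---|
| Within-arm McNemar test, no variable | End of the OHIP-14 sentence; the opening clause, which dichotomises each question, is missing | No McNemar test |
| REU described by arm | Same sentence, on REU | Same form, but on VAS |
| Change compared between arms, t-test or Mann-Whitney | Same sentence, following REU | Same contrast and tests, on VAS change |

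Two things differ from Section 13.1.1: the variable (REU instead of VAS sensitivity) and the added McNemar sentence. The contrast and the test family agree.

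**Step 2. Can McNemar be applied to the primary endpoint?** McNemar needs a yes/no outcome at both visits. The only dichotomy defined for analysis is the one for OHIP-14 questions in Section 13.1.2. The score of 7 in Section 6 is an entry threshold, not a response definition. As written, the test cannot be run on the sensitivity score.

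**Step 3. Does the conflict affect the sample size?** Inputs from Section 13.2: difference 6.5 − 4.5 = 2.0 points, SD of change 1.4, two-sided alpha 0.05, power at least 80%, 5% loss, 15 per arm.

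- The noncentral t calculation for exactly 80% power gives 8.76, so 9 per arm. With 5% loss, 9/0.95 = 9.5, so 10 per arm. The stated 15 is therefore not the 80% solution, but it does meet the stated minimum.
- At 15 per arm, SE = 1.4 × √(2/15) = 0.511, df = 28, and power is 96.5%. The 95% CI half-width is 2.048 × 0.511 = 1.05 points.
- At 14 per arm, power is 95.3% and the half-width is 1.09.

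The sample size rests on the between-arm VAS comparison of Section 13.1.1, so correcting the row leaves it unchanged.

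**Step 4. How much does the open choice of test matter?** Whole-point change scores were simulated with SD 1.4, 15 per arm and 20,000 trials per setting.

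| True difference | t-test significant | Mann-Whitney significant | Tests disagree | Either significant |
|---|---|---|---|---|
| 0 | 5.0% | 4.6% | 1.6% | 5.6% |
| 1.0 | 45.4% | 42.8% | 6.1% | 47.2% |
| 2.0 | 96.0% | 95.0% | 1.6% | 96.3% |

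Even freely taking the better of the two tests gives a type I error of 5.6%.

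**Step 5. Would ANCOVA be a better single test?** Hold the SD of change at 1.4. With baseline SD sb and correlation r, the week-4 SD is sp = r·sb + √((r·sb)² − sb² + 1.96). The residual SD is sp·√(1 − r²), the variance is multiplied by (1 + 1/26), and df = 27. The plan gives no r and no baseline SD for this population. Section 1.1.2 reports a pre-treatment SD of 1.4 in the dexamethasone study on which Section 13.2 bases the sample size. That may be too high here, because entry requires a score of at least 7. An SD of 1.0 is assumed as the lower value.

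| Baseline SD | r | Residual SD | Power |
|---|---|---|---|
| 1.0 | 0.3 | 1.264 | 98.4% |
| 1.0 | 0.5 | 1.386 | 96.2% |
| 1.0 | 0.6 | 1.399 | 95.9% |
| 1.4 | 0.5 | 1.212 | 99.0% |
| 1.4 | 0.6 | 1.344 | 97.1% |

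Against 96.5% for the t-test, ANCOVA runs from a slight loss to a modest gain.

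**Step 6. The OHIP-14 dichotomy in its proper place.** Section 13.1.2 counts the two lowest answers on a not-at-all-to-extremely scale as response, and its example asks about feeling isolated. The OHIP-14 in Appendix 5 runs from Never to Very Often and has no such item. The response labels in Section 13.1.2 appear only on items 4 and 6 of the visit forms in Appendices 3 and 4.

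**The case against.** The strongest defence is that Section 13.1.1 is correct, that the endpoint and sample-size rows of the same table point to the sensitivity score, and that a SAP will follow. That stands as a limit on the practical risk. It does not remove the conflict: the provision for a SAP covers changes to the plan in Section 13 and does not correct the synopsis.

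A reader might infer that the row tests only within arms and so cannot answer A versus B. The documents do not support that, because the third sentence is already a between-arm comparison. A reader might also infer that the trial has no valid primary analysis; Section 13.1.1 supplies one. Finally, the unsettled choice between two tests might be read as a serious threat to the error rate. The 5.6% in Step 4 shows that it is a minor missing rule, which the later SAP could still supply.

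**Conclusion.** The row is wrong as written and should be fixed. It names a secondary endpoint where the primary one belongs and carries a McNemar test that lost its variable. This is a contradiction to correct, not a missing analysis, and no sample size or error rate changes because of it. That the third sentence refers to REU is a reading from context, since it follows the REU sentence and names no variable of its own. The power figures depend on the Section 13.2 inputs, and the ANCOVA figures also on the assumed correlation and baseline SD. The OHIP-14 mismatch is a separate correction to a secondary endpoint and adds nothing to the weight of this point.

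**What to change.** - **Synopsis row:** replace the text with the Section 13.1.1 analysis: the between-arm difference in change in worst sensitivity over the past week, baseline to week 4, two-sided 0.05, with the estimate and 95% CI. Leave the McNemar and REU sentences in Section 13.1.2 only.
- **Same edit, in the row and in Section 13.1.1:** name one primary test. The t-test on change is adequate. ANCOVA of the week-4 score on arm and baseline is an alternative that uses data already collected and costs one degree of freedom. Make Mann-Whitney on change a fixed sensitivity analysis.
- **Separately, in Section 13.1.2:** restate the OHIP-14 response definition and its example on the scale and items in Appendix 5.

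The cost is one synopsis row and a sentence each in Sections 13.1.1 and 13.1.2, best done before the SAP is written. No visits, data or subjects are added.

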1 BACKGROUND

Oral Inflammatory Ulcerative Diseases are relatively common conditions seen in oral medicine practices. These include oral lichen planus (OLP), pemphigus vulgaris, mucous membrane pemphigoid (MMP) and oral chronic graft versus host disease (cGVHD).

Oral lichen planus

Oral lichen planus (OLP) is a benign, chronic condition that occurs in 1 to 2% of adults¹. Middle-aged women are twice as likely to be affected as men. OLP may be associated with a variety of systemic and local conditions and medication use such as thiazide diuretics, angiotensin converting enzyme (ACE) inhibitors, beta blockers, gold salts, sulfasalazine, sulfonyleureas and penicillamine. Biologic agents such as tumor necrosis factor (TNF) alpha inhibitors may also cause lichen planus-like eruptions². Amalgam and composite restorations may cause localized contact lichenoid hypersensitivity reactions possibly to mercury and formaldehyde.

OLP can affect any mucosal surface, and most commonly affects the buccal mucosa and tongue bilaterally. OLP can present with three distinct forms: reticular/keratotic, erosive/erythematous, and ulcerative forms. The reticular/keratotic form, characterized by Wickham striae, is the most common form and is often asymptomatic. Occasionally patients will report discomfort and describe the buccal mucosa as “rough,” “thick,” or “tight”. The erosive/erythematous form typically presents as desquamative gingivitis. Patients may complain of discomfort while eating acidic, spicy or crunchy food. The ulcerative form is the most severe and presents as shallow ulcerations that have a yellow fibrin membrane on the surface. Often, there is a combination of the three forms at different sites, or at different times. Most patients exhibit a characteristic bilateral and symmetric distribution of lesions, typically involving the buccal mucosa, dorsum and ventral surfaces of the tongue and/or gingiva.

The diagnosis of oral lichen planus is based primarily on clinical characteristics, although biopsy may be indicated when the presentation is not typical (e.g. unilateral presentation, or lack of reticulation features)^{3,4}. Histopathological examination demonstrates a lymphocytic band of variable thickness at the interface and degeneration or loss of the basal cell layer.

Mucous membrane pemphigoid

Mucous membrane pemphigoid is an autoimmune vesiculobullous disease associated with increased frequency of HLA-DQB1*0301 and characterized by autoreactive antibodies, usually IgG and sometimes IgA that target antigens in the epithelium-attachment complex resulting in subepithelial blistering and mucosal fragility⁵. MMP may involve the larynx, nose, eyes, and genital mucosa. One of the major complications is conjunctival scarring that can lead to blindness (hence the older term “cicatricial pemphigoid”). Scarring may also involve the larynx and esophagus, but fortunately is uncommon in the oral mucosa.

The oral mucosal lesions almost always affect the gingiva leading to bright red or “desquamative gingivitis”. This is caused by epithelium peeling off the gingiva leaving only exposed connective tissue which is the basis for a positive Nikolsky sign. Ulcers may develop on the gingiva and elsewhere in the mouth such as the palatal, buccal and tongue mucosa. Biopsy of a perilesional area for histopathological examination and direct immunofluorescence (DIF) studies is essential for a definitive diagnosis; DIF shows deposition of IgG, C3 and sometimes IgA at the basement membrane zone.

Management includes topical treatment with corticosteroids or tacrolimus. Systemic agents such as prednisone, dapsone, azathioprine, tetracycline, nicotinamide and cyclophosphamide may be

required for management of refractory oral MMP. When the skin is involved, the diagnosis is bullous pemphigoid.

Pemphigus vulgaris

Pemphigus vulgaris (PV) is an uncommon autoimmune vesiculo-bullous disorder that affects mainly older adults and was fatal in the pre-steroid era. PV has a predilection for Ashkenazi Jews (who exhibit a high frequency of HLA-B38 or HLA-B35), Arabs and others individuals from the Mediterranean region. Different HLA subtypes are implicated in PV in Caucasians and Asians. Autoantibodies, mostly IgG are directed towards the inter-epithelial cementing substance, leading to intra-epithelial blistering⁶. Oral ulcers, present in 95% of patients, are often the first sign of PV with skin lesions developing later. Oral lesions are characterized by painful, irregular, erythematous depressed erosions with whitish tissue tags at the edges; yellow ulcerations may also be present. The most common affected oral sites are the hard and soft palatal mucosa (likely because of physiologic trauma from swallowing), gingiva (also presenting as “desquamative gingivitis”), buccal mucosa and tongue. Diagnosis is established through a perilesional tissue biopsy for histopathologic evaluation and DIF which shows intercellular deposition of IgG.

Topical corticosteroid therapy or topical tacrolimus are the mainstays of therapy. More severe or refractory cases require systemic agents such as prednisone, mycophenolate mofetil, azathioprine and cyclosporine. For severe cases and if the skin is involved, specialist referral is indicated and treatment is generally with prednisone, rituximab (a monoclonal antibody), IVIg, or extracorporeal photopheresis.

Chronic graft-versus-host disease

Chronic graft-versus-host disease remains a significant complication of allogeneic hematopoietic cell (bone marrow) transplantation and continues to be the leading cause of non-relapse mortality. The oral cavity is affected in around 80% of cases.⁷ The spectrum of oral manifestations in cGVHD includes reticular white lichen planus-like changes with erythema and minimal ulceration that affects both the keratinized and non-keratinized mucosa. Patients typically complain of sensitivity to spicy, acidic food or strongly flavored products. Topical therapy is similar to that for OLP. Based on the NIH ancillary therapy and supportive care guidelines, initial therapy for most patients is with dexamethasone solution 0.5mg/5mL; patients are instructed to swish/gargle for 4-6 minutes then spit, 4-6 times per day and to avoid eating or drinking for 10-15 minutes using the medication. Other topical steroids with higher potency may also be prescribed (e.g., clobetasol).

1.1 Overview of Clinical Studies

1.1.1 Management of Oral Inflammatory Ulcerative Diseases

Available therapies for Oral Inflammatory Ulcerative Diseases are aimed at managing symptoms through the reduction of inflammation. The mainstay of therapy remains use of topical corticosteroids which can be delivered in various vehicles including gels and solutions^{1,8,9}. A response to treatment with midpotency corticosteroids (e.g., triamcinolone acetonide 0.1%), potent fluorinated corticosteroids (e.g., fluocinolone acetonide 0.1% and fluocinonide 0.05%), and super-potent halogenated corticosteroids (e.g., clobetasol propionate 0.05%), has been reported in 30–100% of treated individuals¹⁰⁻¹⁵.

One of the challenges in applying topical corticosteroids is the lack of adherence to the oral mucosa for an adequate duration for the medication to be locally absorbed. Numerous obstacles are encountered when a topical steroid is prescribed to treat Oral Inflammatory Ulcerative

Diseases, including the presence of saliva, changes in taste, poor tissue penetration, enzymatic degradation, and the need for frequent dosing, all of which may negatively affect patient compliance¹⁶. One approach to develop more efficacious and safer therapies could be inflammation-targeting drug delivery to achieve high drug concentrations locally at the site of inflammation with minimal exposure of healthy or distant tissues.

Use of topical steroids for Oral Inflammatory Ulcerative Diseases may lead to the development of secondary candidiasis in 11-47% of patients, which requires antifungal therapy^{13,17,18}. Fluconazole 200 mg once weekly has been shown to be an effective prophylaxis measure to prevent oral candidiasis infection¹⁹⁻²¹. Although there are some reports of systemic absorption and adrenal suppression from super-potent topical steroids in the treatment of chronic dermatologic disorders, adrenal suppression is uncommon even in long-term oral application of topical corticosteroids such as fluocinonide and clobetasol²²⁻²⁴. Systemic absorption from topical steroids has been reported and it is thought that absorption of small amounts through the oral mucosa can take place, but clinical experience and laboratory studies have shown this not to be of clinical significance in almost all cases²⁵. Gonzalez-Moles et al. reported two cases of moon facies (2/30) and two cases of hirsutism (2/30) secondary to long-term use (> 4 weeks) of clobetasol 0.05% solution for the treatment of oral erosive lesions. All cases resolved upon discontinuation of the medication and/or reduction in frequency of administration. Other side effects reported include nausea, mucosal atrophy, xerostomia, halitosis and delayed healing^{25,26}.

